9.1.3.2 Administration of NIMP

The IWRS will assign the required NIMP (TCS) kit numbers for each subject at each dispensing visit. The NIMP will be provided as mometasone furoate, 0.1% cream in kit sizes of 180–225 g every 2 weeks. If needed, additional NIMP kit(s) may be dispensed to the subject at a scheduled or unscheduled visit at the investigator's discretion. The amount of additional NIMP dispensed must be recorded in the eCRF.

Subjects will be instructed to apply a thin film of the dispensed TCS (Europe: Class 3 [potent]; US: Class 4 [mid-strength]) once daily to active lesions, as needed. The TCS should be discontinued when control is achieved; discontinuation should preferably be gradual and the maximum duration of treatment should not exceed 3 weeks. The safety and appropriateness of continued or repeated courses of TCS therapy will be monitored and supervised by site staff.

From randomisation (Week 0) through Week 30, the TCS will be dispensed and the subject must return used and unused TCS tubes at each subsequent trial visit, to assess the amount of medication used. The subjects must be instructed by the site staff on the importance of returning all used and unused TCS tubes. The site staff will return used and unused TCS tubes to the contract manufacturing organisation (CMO). The TCS tubes will be weighed at the CMO before shipment to the trial sites and again upon return.

An additional, lower potency TCS or TCI may be used at the investigator's discretion on areas of the body where use of the supplied TCS is not advisable such as areas of thin skin (face, skin fold areas, genital areas, etc.) or on areas where continued treatment is considered unsafe. The low potency TCS and TCI will not be provided by LEO and will not be weighed, but must be registered in the eCRF as concomitant medications (see Section 9.4).

Further details on NIMP dispensing are provided in a drug handling manual. NIMP administration must be carried out according to these instructions.

9.2 Treatment assignment

Subjects who have been found to comply with all the inclusion criteria and not to violate any of the exclusion criteria will be randomised at baseline (Day 0) to receive treatment with either tralokinumab or placebo. Treatment assignment will be pre-planned according to a computer-generated randomisation schedule in a 2:1 ratio (tralokinumab:placebo) stratified by region (Europe and North America) and baseline disease severity (IGA of 3 or 4).

Trial ID: LP0162-1339	Date: 29-Aug-2018	Version: 4.0
		Page 51 of 129

Subjects will be re-randomised to continuation treatment at Week 16. The treatment during this period will depend on the regimen received in the initial treatment period and the subject's clinical response at Week 16. Subjects randomised to tralokinumab who have a clinical response at Week 16 (i.e. IGA 0/1 or EASI75), will be re-randomised to the continuation treatment period in a 1:1 ratio (tralokinumab Q2W:tralokinumab Q4W) stratified by region and IGA response at Week 16 (IGA 0/1 or IGA >1). Subjects randomised to placebo who have a clinical response at Week 16 will continue on placebo. Subjects in either the tralokinumab or placebo group who have not achieved a clinical response at Week 16 will receive tralokinumab Q2W in the continuation treatment period.

IWRS will be used to control randomisation, re-randomisation, and stratification factors, along with IMP supply chain and expiry tracking, and for dispensing and return of NIMP (TCS).

9.2.1 Blinding

This is a double-blinded trial in which tralokinumab and placebo are visually distinct from each other. Neither the subject nor any of the investigator or LEO staff who are involved in the treatment or clinical evaluation and monitoring of the subjects will be aware of the treatment received.

The packaging and labelling of the IMPs will contain no evidence of their identity. IMP is packed in identical boxes, with non-sequential kit numbers to ensure that unblinding does not occur during shipment and handling of the drug.

Since tralokinumab and placebo are visually distinct and not matched for viscosity, IMP will be handled and administered by a qualified, unblinded HCP (trained site staff) at the site who will not be involved in the management of trial subjects and who will not perform any of the assessments.

If treatment allocation for a subject becomes known to the investigator or other trial staff involved in the management of trial subjects, LEO must be notified immediately.

Should an issue arise with the IMP (e.g., damaged kit or syringe that has been assigned to a subject prior to administration, or any other unexpected event with the kit or syringe [e.g., a malfunction during IMP administration]), the unblinded HCP at the site will contact the clinical research associate (CRA) to determine whether any specific actions are required.

Trial ID: LP0162-1339	Date: 29-Aug-2018	Version: 4.0
		Page 52 of 129

The trial site will maintain a written plan detailing which staff members are blinded/unblinded and the process of IMP administration used to maintain the blind.

To support submission for marketing approval, an analysis of trial data up to and including visit 19 (Week 32) will be performed and will require unblinding of data. To perform this analysis, an Analysis Group consisting of a Medical Expert, a Statistician, a Statistical Programmer and a Medical Writer will be unblinded to individual subject treatment allocation following database lock for the 32-week data. All staff involved in the conduct of the trial will remain blinded to treatment allocation for the entire duration of the trial. This principle will be applied to all investigator staff and to staff employed by the sponsor except for those who are directly involved in the execution of the analysis. See Section 12.3.11 for details regarding the statistical aspects of the analysis of data up to Week 32.

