All subjects will use an emollient twice daily (or more, as needed) for at least 14 days before randomisation and will continue this treatment throughout the trial (including safety follow-up). Subjects will initiate emollient treatment no later than the Week -2 visit. On lesional skin, emollients should only be applied at times where TCS is not applied (i.e., emollients and TCS should not be used on the same areas at the same time of day); on TCS-untreated areas, the emollients may be applied at all times.

Initial treatment period (Week 0 to Week 16)

Following the screening period, approximately 369 subjects will be randomised 2:1 to one of the following groups stratified by region (Europe and North America) and baseline disease severity (IGA 3 or 4):

- Tralokinumab 600 mg (4 mL) at baseline, then 300 mg (2 mL) Q2W.
- Placebo (4 mL) at baseline, then placebo (2 mL) Q2W.

Doses will be administered at the trial site by subcutaneous (SC) injection.

Subjects in both treatment groups will apply a thin film of a supplied TCS (Europe: Class 3 [potent]; US: Class 4 [mid-strength]) once daily to areas with active lesions as needed; lower potency TCS or TCI may be prescribed if needed on body areas where the supplied TCS is not advisable or on areas where continued treatment with TCS is considered unsafe. Topical therapy will be discontinued when control is achieved; discontinuation should preferably be

Trial ID: LP0162-1339	Date: 29-Aug-2018	Version: 4.0
		Page 36 of 129

gradual. The safety and appropriateness of continued or repeated courses of TCS therapy will be monitored and supervised by site staff.

Continuation treatment period (Week 16 to Week 32)

At Week 16, all subjects will be assigned to continuation treatment that will carry on until Week 32 (the last dose of IMP will be administered at Week 30). The treatment during the continuation period will depend on the regimen received in the initial treatment period and on the subject's clinical response at Week 16. Clinical response is defined as IGA of 0 or 1 or EASI75.

Subjects randomised to tralokinumab in the initial treatment period and with a clinical response at Week 16 will be re-randomised 1:1 to one of the following Q2W maintenance regimens stratified by region and IGA response at Week 16 (IGA 0/1 or IGA >1):

- Tralokinumab 300 mg (2 mL) ('tralokinumab Q2W').
- Alternating dose administrations of tralokinumab 300 mg (2 mL) and placebo (2 mL) ('tralokinumab Q4W').

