Subjects randomised to placebo in the initial treatment period and with a clinical response at Week 16 will continue to receive placebo Q2W in the continuation treatment period.

Subjects randomised to tralokinumab or placebo in the initial treatment period who do not fulfil either of the criteria for clinical response at Week 16 will receive tralokinumab Q2W in the continuation treatment period.

All subjects will stay on the TCS regimen during the continuation treatment period.

Safety follow-up period (Week 32 to Week 46)

Subjects, except those who enter the long-term extension trial (LP0162-1337, ECZTEND, see below), will complete a 14-week off-treatment follow-up period for the assessment of safety, PK, and anti-drug antibodies (ADA).

Long-term extension trial (selected countries)

Eligible subjects may be invited to enter a long-term extension trial conducted under a separate protocol (LP0162-1337, ECZTEND). Subjects who transfer to ECZTEND must have had their last visit in the treatment period (Week 32 under the current protocol).

Trial ID: LP0162-1339	Date: 29-Aug-2018	Version: 4.0
		Page 37 of 129

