7.4 Scientific rationale for trial design

The trial is designed to evaluate the efficacy and safety of tralokinumab in combination with TCS therapy versus placebo with TCS in subjects with moderate-to-severe AD. The trial endpoints have been selected to evaluate the efficacy of tralokinumab in improving the severity and extent of AD including both objective signs of disease and subjective symptoms (e.g. itch) as well as HRQoL. The two primary efficacy endpoints IGA score of 0 or 1 and EASI75 are recognised as important endpoints in clinical trials in AD by regulators in the US and EU, respectively.

The planned trial design is considered appropriate for evaluating the trial objectives, as the double-blind conditions regarding the subject's treatment (tralokinumab or placebo) are maintained and the possible observer bias regarding treatment effects are minimised.

Trial ID: LP0162-1339	Date: 29-Aug-2018	Version: 4.0
		Page 38 of 129

Stratification by region (Europe and North America) and baseline disease severity (IGA 3 or 4) in this multi-centre trial will provide a strong basis for generalisation of the findings to the target patient population. Further, the trial population will comprise male and female subjects to explore effects between genders and across the adult age range.

By using a placebo-controlled parallel group design for the initial treatment period, superiority of tralokinumab in combination with TCS versus placebo in combination with TCS can be investigated, hereby adding to the knowledge needed for positioning tralokinumab in the AD treatment pathway.

The most important inclusion criterion for entry into the trial is an established diagnosis of AD (as defined by the Hanifin and Rajka 1980 criteria for AD)(21) at screening and a history of AD for at least one year, to ensure correct diagnosis and rule out differential diagnosis. A prerequisite for inclusion into the trial is a documented history of topical AD treatment failure (due to inadequate response), to ensure that the subject is candidate for systemic treatment. Subjects for whom topical treatment with TCS are medically inadvisable may not be enrolled as TCS therapy will be administered in this trial.

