10.3.1.2 Eczema Area and Severity Index

The EASI is a validated measure used in clinical practice and clinical trials to assess the severity and extent of AD (26). Details on the scoring of severity and extent of AD according to EASI are included in the efficacy assessment & C-SSRS manual.

The EASI score will be assessed according to the schedule of procedures (Section 4). The assessment will be based on the condition of the disease at the time of evaluation and not in relation to the condition at a previous visit. Whenever possible, the EASI should be assessed by the same investigator at each visit to reduce inter-rater variability.

Trial ID: LP0162-1339	Date: 29-Aug-2018	Version: 4.0
		Page 66 of 129

The EASI is a composite index with scores ranging from 0 to 72, with higher values indicating more severe and/or more extensive condition. The index will be calculated as shown in Panel 7. Briefly, the investigator will assess the severity of 4 AD disease characteristics (erythema, induration/papulation, excoriation, and lichenification) on the 4 body regions (head/neck, trunk, upper extremities, lower extremities); severity will be assessed according to the scale shown in Panel 8. For each body region, a severity sum score will be calculated which will be multiplied by an area score (Panel 8) and by a weighting factor. The EASI score equals the sum of the scores obtained for each body region (Panel 7).

Panel 7 Calculation of the Eczema Area and Severity Index

Body region	Erythema	Induration/ papulation	Excoriation	Lichenification	Area score	Weighting factor	Score
Head/neck	(SS +	SS +	SS +	SS)	× AS	× 0.1	
Trunk	(SS +	SS +	SS +	SS)	× AS	× 0.3	
Upper extremities	(SS +	SS +	SS +	SS)	× AS	× 0.2	
Lower extremities	(SS +	SS +	SS +	SS)	× AS	× 0.4	
	The	e EASI sco	re is the su	m of the 4	body regio	on scores	(range 0-72)

Abbreviations: AS, area score; EASI, Eczema Area and Severity Index; SS, severity score. Modified from (27).

Panel 8 EASI severity score scale and area score scale

Severity score scale		
0	None/absent	
1	Mild	
2	Moderate	
3	Severe	

Half-points (0.5; 1.5; 2.5) may also be used.

Area score scale		
0	0% affected area	
1	1% to 9% affected area	
2	10% to 29% affected area	
3	30% to 49% affected area	
4	50% to 69% affected area	
5	70% to 89% affected area	
6	90% to 100% affected area	

Abbreviations: EASI, Eczema Area and Severity Index.

Trial ID: LP0162-1339	Date: 29-Aug-2018	Version: 4.0
		Page 67 of 129

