12.3.9 Analysis of safety

The analyses of safety will be based on the safety analysis set. The reporting of safety data will be presented separately for initial treatment and continuation treatment.

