12.3.9.1 Adverse events

To assess the safety of tralokinumab in combination with TCS when used to treat moderate-to-severe AD for 32 weeks, the frequency of AEs and SAEs are included as additional secondary endpoints.

AEs will be coded during the course of the trial according to Medical Dictionary for Regulatory Activities (MedDRA). AEs will be presented by preferred terms and primary system organ class (SOC).

Treatment-emergent AEs will be summarised, however, all AEs recorded during the course of the trial will be included in the subject data listings. An event will be considered treatment-emergent if started after the first use of IMP or if started before the first use of IMP (applicable if subject had a wash-out) and worsened in severity thereafter. The tabulations described in the following will only include the treatment-emergent events. In each of the tabulations, AEs will be defined by MedDRA preferred terms within primary SOC.

An overall summary of the number of treatment-emergent AEs and the number (percentage) of subjects with any treatment-emergent AEs, deaths, SAEs, premature discontinuations from the trial due to AEs, treatment-related AEs and severe AEs will be presented.

The number of AEs and the number of subjects experiencing each type of AE will be tabulated by treatment group. The percentage of subjects with AEs in the initial treatment period will be compared between treatment groups by a chi-square test or Fisher's exact test (if expected cell count <5).

Trial ID: LP0162-1339	Date: 29-Aug-2018	Version: 4.0
		Page 100 of 129

The severity for each type of AE will be tabulated by treatment group.

The causal relationship to IMP and NIMP (TCS) for each type of AE will be tabulated by treatment group.

Related AEs are defined as AEs for which the investigator has not described the causal relationship to IMP as 'not related'. The number of related AEs and the number of subjects experiencing each type of related AE will be tabulated. The percentage of subjects with related AEs in the initial treatment period will be compared between treatment groups by a chi-square test or Fisher's exact test (if expected cell count <5).

SAEs and AESIs will be evaluated separately. A narrative for each SAE will be given. AESIs and AEs leading to withdrawal from trial or permanent discontinuation of IMP will be tabulated and listed.

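### Section 9.2.1 claims a blind the design cannot give: in Weeks 16–32 the investigator can deduce the current treatment of every Week 16 non-responder, about 63–68% of randomised subjects on the planning rates

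*Protocol*

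**What the plan says.** **The assignment rule.** Protocol Section 7.1 defines response: "Clinical response is defined as IGA of 0 or 1 or EASI75". Subjects from either initial arm "who do not fulfil either of the criteria for clinical response at Week 16 will receive tralokinumab Q2W in the continuation treatment period". Section 9.2 repeats this for those "who have not achieved a clinical response at Week 16 will receive tralokinumab Q2W in the continuation treatment period". This step involves no randomisation. Only tralokinumab responders are re-randomised (1:1, Q2W or Q4W), and placebo responders stay on placebo.

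**Who knows the response.** IGA and EASI are investigator assessments. For EASI, Section 10.3.1.2 says that "the investigator will assess the severity of 4 AD disease characteristics". The Section 4 schedule has both scored at baseline and at Week 16, and Appendix 3D gives the site immediate access to data entered in the eCRF. Nothing in the protocol masks response status.

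**The blinding claims.** Section 9.2.1 opens with a general statement that the subject, and the investigator and sponsor staff who treat, evaluate or monitor subjects, will not know the treatment given. Later it adds: "All staff involved in the conduct of the trial will remain blinded to treatment allocation for the entire duration of the trial". Section 7.4 says that "the double-blind conditions regarding the subject's treatment (tralokinumab or placebo) are maintained and the possible observer bias regarding treatment effects are minimised". Section 12.3.11 repeats the claim for the whole trial, and Section 7.2 relies on the IWRS for continued blinding.

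**The use of continuation data.** Section 12.3.9: "The reporting of safety data will be presented separately for initial treatment and continuation treatment". Section 12.3.9.1: "The causal relationship to IMP and NIMP (TCS) for each type of AE will be tabulated by treatment group". Section 12.3.7 summarises Week 32 IGA, EASI and SCORAD responses by continuation treatment group.

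**The concern.** An IWRS can hide which kit is active. It cannot hide a treatment that follows with certainty from a published rule and two scores the investigator has just recorded. For a subject who meets neither criterion, the investigator knows at Week 16 that tralokinumab Q2W follows. The statements in 9.2.1, 7.4 and 12.3.11 carry no exception for this.

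What is at stake is how the 32-week data are described and read. In the continuation period, investigator judgements of AE severity and causality, and IGA, EASI and SCORAD, are made with current treatment known for non-responders and masked for responders. Section 9.1.3.1 lists only three continuation regimens (Q2W, Q4W and placebo), and the tables are by treatment group. A reader told that the whole trial was double-blind would take all columns as rated under the same conditions. Section 9.2.1 also requires the sponsor to be told at once if allocation becomes known to the investigator, and does not say how that applies when current treatment follows from the rule.

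**Working it through.** **Inputs.** From Sections 7.2 and 12.1: 369 subjects, 246 on tralokinumab and 123 on placebo; about 40% of tralokinumab subjects expected to be re-randomised as responders; IGA 0/1 rates of 30% and 15%; EASI75 rates of 40% and 15%. The protocol does not give the placebo rate for the composite (IGA 0/1 or EASI75).

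**Step 1: the plan's own figure.** The protocol gives no figure for the share of subjects whose treatment can be deduced. Its power figures rest on the same rates and reproduce, using the two-proportion normal formula with pooled variance under the null, no continuity correction, two-sided 5%:
- IGA 0/1, 30% v 15%: pooled rate (18.45 + 73.8)/369 = 0.25. Null SE = √(0.25 × 0.75 × (1/123 + 1/246)) = 0.0478. Alternative SE = √(0.15 × 0.85/123 + 0.30 × 0.70/246) = 0.0435. z = (0.15 − 1.96 × 0.0478)/0.0435 ≈ 1.29, so power is 90.2% (stated 90%).
- EASI75, 40% v 15%: the same formula gives 99.96% (stated above 99.9%).

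**Step 2: bounds for the placebo composite rate.** If the two 15% component rates overlap fully, the composite is 15%. If they do not overlap at all, it is 30%. The truth under the planning rates lies between.

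**Step 3: expected non-responders, ignoring dropout.** N = 246 × (1 − 0.40) + 123 × (1 − p), with p the placebo composite rate.
- p = 0.15: 147.6 + 104.55 = 252.15, or 252/369 = 68.3%.
- p = 0.30: 147.6 + 86.1 = 233.7, or 234/369 = 63.3%.

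**Step 4: allowing for dropout before Week 16.** Assume a fraction d = 5–15% drops out, all from among the non-responders. The share of those continuing is [246(1 − d − 0.40) + 123(1 − d − p)] / [369(1 − d)].

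| d | p = 0.15 | p = 0.30 |
|---|---|---|
| 5% | 66.7% | 61.4% |
| 10% | 64.8% | 59.3% |
| 15% | 62.7% | 56.9% |

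**Step 5: who stays masked.** Tralokinumab responders: 246 × 0.40 = 98.4, split 1:1 into about 49 on Q2W and 49 on Q4W. Placebo responders: 123 × 0.15 = 18 to 123 × 0.30 = 37. An investigator facing a responder cannot tell which of the three regimens applies.

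**Step 6: what can and cannot be deduced.** Non-responders from both arms get the same regimen, so the rule reveals current treatment but not initial allocation. By Section 10.1, assessments at a visit precede IMP administration, so the Week 16 scores are taken before any continuation dose.

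**The case against.** The case for leaving this alone has real substance.

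- **Context of the quoted sentence.** It stands in the paragraph on unblinding the Analysis Group after the 32-week lock, and Section 12.3.11 has the same context. Both can be read as saying only that conduct staff will not be given the allocation codes. That is fair, but the opening paragraph of 9.2.1 makes the general claim about treatment received, and that claim fails for non-responders.
- **The rule is disclosed and deliberate.** Section 5.6 says that everyone except placebo responders will receive tralokinumab after Week 16 and gives this as part of the ethical case. This defends the rule, not the blinding statement.
- **Responders are not in complete ignorance either.** With about 98 tralokinumab and 18–37 placebo responders, a rater can put the chance of active treatment at 98.4/135.3 = 73% to 98.4/116.85 = 84%. The contrast is certainty against a high probability. That softens the concern, but the Q2W or Q4W assignment stays masked in responders.
- **No planned test is touched.** The multiplicity hierarchy covers the initial period, AE percentages are compared by test only there, and the maintenance endpoints are descriptive and confined to responders. This stands.

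The documents do not support several stronger inferences that a reader might draw:
- **That most of the continuation Q2W column is open-label.** This needs non-responders to be pooled with re-randomised Q2W responders, and the protocol does not say they are. Pooling would also make the comparison non-randomised, which would be the larger problem.
- **That patient-reported outcomes are given by people certain of their treatment.** Subjects complete these, and nothing shown says that they are told their response status.
- **That hiding the response classification in the IWRS would restore the blind.** It cannot do so for an investigator who has scored both criteria.

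**Conclusion.** Wrong as written. The unqualified statement in 9.2.1 that evaluating staff will not know the treatment received, echoed in 7.4 and 12.3.11, does not hold in Weeks 16–32 for Week 16 non-responders.

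The size is about 234–252 of 369 randomised subjects (63–68%) before dropout. It rests on the protocol's 40% tralokinumab response and on a placebo composite rate between 15% and 30%, bounded from the stated components. With an assumed 5–15% dropout it is about 57–67% of those continuing. That the investigator knows who responded is inferred from the scoring role and eCRF access; the protocol does not state it, and nothing in the protocol contradicts it.

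The consequence is limited. A reader might infer that the confirmatory results are compromised, and they are not: the Week 16 primary and secondary endpoints, type I error, power and the responder-only maintenance endpoints are unaffected. Exposed are the descriptive continuation-period AE severity and causality tables (12.3.9.1) and the Week 32 summaries by continuation treatment group (12.3.7), which are not restricted to Week 16 responders.

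**What to change.** 1. In Sections 7.4, 9.2.1 and 12.3.11, limit the blinding claim for current treatment to Weeks 0–16 for all subjects and to Weeks 16–32 for Week 16 responders. State that the continuation treatment of non-responders is known by rule, while their initial allocation stays masked.
2. In the continuation-period safety tables and the Week 32 summaries, show non-responders on Q2W separately from re-randomised Q2W responders, labelled as effectively open-label for the investigator. Base any reading of Q2W against Q4W only on the re-randomised responders.

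The cost is protocol and SAP wording and one more set of columns. The downside is that the 32-week data can no longer be described as fully double-blind, and the blinded Q2W group is about 49 subjects. No dose or allocation rule changes.
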